17. SAFETY OUTCOMES

All outputs for safety outcomes will be based on the SAF set.

There will be no statistical comparisons between the treatment groups for safety data, unless otherwise specified with the relevant section.

17.1. ADVERSE EVENTS

Adverse Events (AEs) will be coded using MedDRA central coding dictionary. The version of MedDRA to be used will be specified prior to database lock.

Treatment-emergent adverse events (TEAEs) are defined as AEs that started or worsened in severity on or after the first dose of study medication. Laboratory or ECG findings from procedures or samples drawn prior to the first does of study medication that are assessed/overread after randomization will be considered pre-treatment.

In the case where it is not possible to define an AE as treatment-emergent or not, the AE will be classified by the worst case; i.e. treatment-emergent.

See Appendix 2 for handling of partial dates for AEs.

An overall summary of number of patients within each of the categories described in the sub-section below, will be provided as specified in the shells. The summary AE tables will be presented for overall (up to the end of study for all patients) and separately for data up to week 24 visit (regardless of which treatment duration stratum a patient is randomized into) and data from week 24 up to week 48 visit.

In addition, the number of patients with each of the following AE events will be presented by SOC and PT and summarized by treatment group and different period (i.e. Treatment period (+3

[REDACTED]	[REDACTED]	[REDACTED]	[REDACTED]
[REDACTED]	[REDACTED]	[REDACTED]	[REDACTED]
[REDACTED]	[REDACTED]	[REDACTED]	[REDACTED]
[REDACTED]	[REDACTED]	[REDACTED]	[REDACTED]

days), Follow-up (last dose + 4 days) and Overall). These will also be presented for overall, up to week 24 visit, and from week 24 up to week 48 visit:

- TEAE
- TEAEs causally related to study medication
- Serious TEAEs
- TEAEs with an outcome of death
- TEAEs leading to discontinuation of blinded study medication
- TEAEs leading to withdrawal from study (TEAEs with a diagnosis of COVID-19, TEAEs with no diagnosis of COVID-19)
- TEAEs by maximum severity (Mild, Moderate, Severe)

AEs will be identified by using the “Adverse Events” page of the eCRF. Listings will include TEAEs and Non-TEAEs.

Treatment period is defined as the period from the date and time of first dose up to the last date and time of last dose.

Follow-up is defined as the period from after the date and time of last dose up to the last date recorded on the study.

17.1.1. ALL TEAEs

Incidence of TEAEs will be presented by SOC and PT and broken down further by maximum severity and relationship to study medication.

17.1.1.1. Severity

Severity is classed as mild/ moderate/ severe (increasing severity). TEAEs starting after the first dose of study medication with a missing severity will be classified as severe. If patient reports a TEAE more than once within that SOC/ PT, the AE with the worst-case severity will be used in the corresponding severity summaries.

17.1.1.2. Relationship to Study Medication

Relationship, as indicated by the Investigator, is classed as “unknown”, “unrelated”, “unlikely to be related”, “possibly related” and “probably related” (increasing probability of relationship). A “related” TEAE is defined as a TEAE with a relationship to study medication as “possibly related” or “probably related” to study medication. TEAEs with a missing relationship to study medication will be regarded as “probably related” to study medication. If a patient reports the same AE more than once within that SOC/ PT, the AE with the worst case relationship to study medication will be used in the corresponding relationship summaries.

[REDACTED]	[REDACTED]	[REDACTED]	[REDACTED]
[REDACTED]	[REDACTED]	[REDACTED]	[REDACTED]
[REDACTED]	[REDACTED]	[REDACTED]	[REDACTED]
[REDACTED]	[REDACTED]	[REDACTED]	[REDACTED]

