9.4.2 Safety Analyses

Safety analysis will be based on the safety set.

Adverse events will be analyzed using quantitative and qualitative measures. Treatment-emergent adverse events will be summarized by treatment group for all AEs, related AEs, serious adverse events, deaths, adverse events leading to discontinuation of blinded study medication or to withdrawal from study, adverse events of different severity and adverse events of different chronicity. Treatment-emergent adverse events will be coded using the Medical Dictionary for Regulatory Activities (MedDRA) and summarized by system organ class and preferred term for each treatment group. For selected adverse events, time to first event will be visualized using Kaplan-Meier plots.

Laboratory data will be summarized by each visit including change from baseline. The number of normal, abnormal not clinically significant and abnormal clinically significant values on each parameter will be summarized for change over study using shift tables. All data will be listed and values outside reference ranges will be highlighted in the listings.

Vital signs and continuous parameters from the ECGs will be summarized by each visit including change from baseline. Values outside pre-specified ranges (low, high) or changes exceeding pre-specified limits will be summarized by visit for each parameter. The number of normal, abnormal not clinically significant and abnormal clinically significant values on the ECG overall evaluation will be summarized for change over study using shift tables. All data will be listed and values outside reference ranges will be highlighted in the listings.

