- Mild: An event that is easily tolerated by the patient, causing minimal discomfort and not interfering with everyday activities.
- Moderate: An event that causes sufficient discomfort and interferes with normal everyday activities.
- Severe: An event that prevents normal everyday activities. An AE that is assessed as severe should not be confused with a SAE. Severe is a category utilized for rating the intensity of an event; and both AEs and SAEs can be assessed as severe.

An event is defined as 'serious' when it meets at least one of the predefined outcomes as described in the definition of an SAE, NOT when it is rated as severe.

Assessment of Chronicity

- Single occasion: Single event with limited duration.
- Intermittent: Several episodes of an event, each of limited duration
- Persistent: Event which remained indefinitely.

Assessment of Causality

- The Investigator is obligated to assess the relationship between blinded study medication and each occurrence of each AE/SAE. The AE must be characterized as unrelated, unlikely to be related, possibly related, probably related, or unknown (unable to judge).
 - “Probably related” conveys that there are facts, evidence, and/or arguments to suggest a causal relationship, rather than a relationship cannot be ruled out.
 - “Possibly related” suggests that the association of the AE with the blinded study medication is unknown; however, the AE is not reasonably supported by other conditions.
 - “Unlikely to be related” suggests that only a remote connection exists between the blinded study medication and the AE. Other conditions, including chronic illness, progression or expression of the disease state or reaction to concomitant therapy, appear to explain the reported AE.
 - “Unrelated” is used if there is not a reasonable possibility that the blinded study medication caused the AE.
 - All efforts should be made to classify the AE according to the above categories. The category “unknown” (unable to judge) may be used only if the causality is not assessable (eg, because of insufficient evidence, conflicting evidence, conflicting data, or poor documentation).
- The Investigator will use clinical judgment to determine the relationship.

- Alternative causes, such as underlying disease(s), concomitant therapy, and other risk factors, as well as the temporal relationship of the event to blinded study medication administration will be considered and investigated.

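### A recorded 'unknown' causality is ranked below 'unrelated' and left out of related TEAEs, while a blank field is counted as probably related

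*SAP*

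**What the plan says.** SAP 17.1.1.2 puts four rules into one paragraph.

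- **Order of categories:** the relationship "is classed as “unknown”, “unrelated”, “unlikely to be related”, “possibly related” and “probably related” (increasing probability of relationship". *Unknown* therefore sits at the bottom, under *unrelated*.
- **Definition of related:** "A “related” TEAE is defined as a TEAE with a relationship to study medication as “possibly related” or “probably related” to study medication".
- **Blank field:** "TEAEs with a missing relationship to study medication will be regarded as “probably related” to study medication".
- **Same event reported more than once within SOC/PT:** "the AE with the worst case relationship to study medication will be used in the corresponding relationship summaries".

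Protocol 11.7 (Assessment of Causality) lists the categories as "unrelated, unlikely to be related, possibly related, probably related, or unknown (unable to judge". *Unknown* comes last there and is not placed on a scale of probability. The protocol adds that it "may be used only if the causality is not assessable", giving insufficient or conflicting evidence as examples.

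The related-event summary is required by Protocol 9.4.2: "Treatment-emergent adverse events will be summarized by treatment group for all AEs, related AEs". SAP 17.1 lists it by SOC, PT, treatment group and period, and SAP 17.7 repeats it on the Extended Safety Set. SAP 3.3, which lists changes from the protocol analysis, does not mention the handling of *unknown*.

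**The concern.** A causality field can lack a usable assessment in two ways: it can be empty, or it can hold the answer that causality could not be assessed. The SAP sends the first to the top of its scale and the second to the bottom. Under the protocol, *unrelated* is a finding that there is no reasonable possibility of causation. *Unknown* is the absence of a finding, so placing it beneath *unrelated* turns missing information into the strongest evidence against a relationship.

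The SAP's other rules for doubtful safety data go the conservative way. Missing severity becomes severe (17.1.1.1), unclear treatment emergence becomes treatment-emergent (17.1), and doubt about whether a patient was treated is resolved as treated (5.8). *Unknown* causality is the exception.

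Safety reporting is descriptive, with no between-group comparisons unless specified (SAP 17). The category definitions therefore decide what a reader of the related-TEAE tables sees.

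**Working it through.** The plan states no figure on this point, so there is none to reproduce. The check applies the rules to possible sets of causality entries, then gives a range under an assumed frequency.

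**Step 1. Apply the rules.** Inputs are the four rules of SAP 17.1.1.2. For one patient and one SOC/PT: set a blank to *probably*; take the highest category on unknown < unrelated < unlikely < possibly < probably; call the result related if it is *possibly* or *probably*. The last column instead counts *unknown* as related, as a blank already is.

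| Entries for one patient and term | Category tabulated (SAP) | Related (SAP) | Related if *unknown* counts as a blank does |
|---|---|---|---|
| unknown | unknown | no | yes |
| blank | probably | yes | yes |
| unknown, unrelated | unrelated | no | yes |
| unknown, unlikely | unlikely | no | yes |
| unknown, possibly | possibly | yes | yes |
| unrelated | unrelated | no | no |

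Three cases move into related and none moves out. Relative to the SAP's treatment of blanks, the related count is therefore equal or lower in every case.

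**Step 2. Separate the two rules.** The low rank does not itself lower the SAP's related count: *unknown*, *unrelated* and *unlikely* are all outside its definition of related. The definition produces the difference in the related tables. The rank acts in the relationship breakdown (SAP 17.1.1): rows 3 and 4 are tabulated as *unrelated* and *unlikely*, and the *unknown* event no longer shows.

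**Step 3. Size.** Planned arm sizes are 500 ensifentrine and 300 placebo (Protocol 1.1, Treatment Groups and Duration). Let p be the proportion of patients with an *unknown* TEAE and no possibly related, probably related or blank one in the same table cell. The documents do not give p, so it is an assumption, taken as equal in both arms. Patients added to related in an arm = p × arm size.

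| Assumed p | Ensifentrine (500 × p) | Placebo (300 × p) |
|---|---|---|
| 0% | 0 | 0 |
| 0.5% | 2.5 | 1.5 |
| 1% | 5 | 3 |
| 2% | 10 | 6 |
| 5% | 25 | 15 |

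With the same p in both arms, each arm's related percentage rises by p points and the difference between arms does not change.

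**The case against.** **A blank and *unknown* are not the same thing.** A blank is absent data and needs an imputation rule, whereas *unknown* is an answer the investigator gave. Handling them differently can be defended in principle. The SAP gives no reason for doing so, however, and neither an absent nor an inconclusive assessment supports a rank below *unrelated*.

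***Unknown* should be rare.** The protocol asks for every effort to use the other categories. It also describes *possibly related* as a label that "suggests that the association of the AE with the blinded study medication is unknown", where other conditions do not reasonably explain the event. Many uncertain events should therefore fall in *possibly related* and be counted. This stands: it limits the likely size, and the effect may be zero.

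**A reader might infer that the related tables under-count drug-related events.** The documents do not support that. The true causality of an *unknown* event is not available, and the rule for blanks pushes the count up, so the net error against the truth has no fixed sign. The shortfall exists only relative to the SAP's own rule for blanks.

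**A reader might also infer that poorly documented serious or fatal events drop out of the safety record.** They do not. Serious TEAEs, fatal TEAEs and those leading to discontinuation are tabulated whatever their relationship. Protocol 11.7 also requires a causality assessment before an SAE is first transmitted, even when little information is available, although it does not expressly bar *unknown*.

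**Equating *unknown* with *probably related* would be a new error.** Protocol 11.7 keeps *probably related* for events with facts, evidence or arguments pointing to causation. This stands, and it narrows the remedy.

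**Conclusion.** The inconsistency is in the text, and no other section of either document removes it. A recorded *unknown* is placed below *unrelated* and excluded from related TEAEs, while a blank is counted as probably related. This conflicts with the meaning of *unknown* in Protocol 11.7 and with the SAP's worst-case convention.

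There are two consequences. Related-TEAE counts are equal to or lower than they would be if *unknown* were counted as a blank is. In the relationship breakdown, an *unknown* event disappears behind *unrelated* or *unlikely* for the same patient and term.

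The size cannot be fixed from the documents. The assumed range of 0 to 5% corresponds to 0 to 25 of 500 ensifentrine and 0 to 15 of 300 placebo patients, using planned randomized numbers; the analysed safety set may be smaller. The all-TEAE, serious, fatal and discontinuation tables and all efficacy results are unaffected.

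**What to change.** Amend SAP 17.1.1.2 before unblinding, so that the coding is not chosen with the arms in view:

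1. Take *unknown* off the bottom of the ordered scale and rank it above *unlikely to be related* for worst-case selection.
2. Count *unknown* as related in the related-TEAE summaries, in line with missing, but do not relabel it *probably related*.
3. Show *unknown* as its own row in the relationship breakdown.
4. Add a footnote with the number of *unknown* events per arm, so that the count with and without them is visible.

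The cost is a short text change, one recode, and a row and footnote in the table shells. No new data are needed. The downside is a slightly higher related-AE count in both arms if *unknown* is used.

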17.1.2. TEAEs LEADING TO DISCONTINUATION OF STUDY MEDICATION

TEAEs leading to discontinuation of study medication are AEs recorded as “Study Treatment Permanently Discontinued” on the “Adverse Events” page of the eCRF.

For TEAEs leading to discontinuation of study medication, summaries of incidence rates (frequencies and percentages) by SOC and PT will be prepared.

17.1.3. SERIOUS ADVERSE EVENTS

Serious adverse events (SAEs) are those events recorded as “Serious” on the “Adverse Events” page of the eCRF. A summary of serious TEAEs by SOC and PT and by treatment group and different period (i.e. Treatment period, Follow-up and Overall) will be prepared.

17.1.4. ADVERSE EVENTS LEADING TO DEATH

TEAEs leading to Death are those events which are recorded as “Fatal” on the “Adverse Events” page of the eCRF. A summary of TEAEs leading to death by SOC and PT will be prepared.

17.2. LABORATORY EVALUATIONS

Results from the central laboratory (or local laboratory where this is required) will be included in the reporting of this study for chemistry, hematology and viral serology. A list of laboratory assessments to be included in the outputs is included in the Appendix 3 of the study protocol. The handling of Russian laboratories is detailed in Section 6.10 of the SAP.

Presentations of all laboratory tests will use either conventional or standard international (SI) units. However, certain laboratory tests will also be presenting using US units, including liver tests. Laboratory evaluations will be presented separately for 24-week and 48-week strata.

The handling of re-test and unscheduled measurements is detailed in Section 6.4 of the SAP.

The following summaries will be provided for chemistry and hematology data:

- Actual and change from baseline by visit (for quantitative measurements)
- Incidence of abnormal values according to normal range criteria
- Shift from baseline according to normal range criteria (for quantitative measurements and categorical measurements)
- Shift from baseline according to markedly abnormal criteria (for quantitative measurements and categorical measurements)
- Listing of patients meeting markedly abnormal criteria

Viral serology, COVID-19 sample, chemistry and hematology will be listed. The original reference ranges recorded by the local sites or provided by InVitro used for chemistry and hematology parameters will be included in the listing.

17.2.1. LABORATORY REFERENCE RANGES AND CLINICALLY SIGNIFICANT ABNORMAL CRITERIA

Quantitative laboratory measurements will be compared with the relevant laboratory reference ranges in SI units and categorized as:

- Low: Below the lower limit of the laboratory reference range.
- Normal: Within the laboratory reference range (upper and lower limit included).
- High: Above the upper limit of the laboratory reference range.

In addition to the high and low quantitative laboratory assignments (as identified by means of the laboratory reference ranges), clinically significant abnormal quantitative chemistry laboratory assessments will also be identified in accordance with the predefined markedly abnormal criteria as presented in Table 4.

If ULN or LLN have " $\leq X$ " or " $\geq X$ " then "X" will be used for analysis and " $\leq X$ " or " $\geq X$ " will only be used in listings.

Table 4: Clinically Significant abnormal criteria for laboratory parameters

Parameter	Clinically Significant Abnormally High Criteria
Alanine Aminotransferase (ALT)	> 3 times Upper Limit of Normal Range
Alkaline Phosphatase	> 3 times Upper Limit of Normal Range
Aspartate Aminotransferase (AST)	> 3 times Upper Limit of Normal Range
Creatinine	>221 $\mu\text{mol/L}$
Gamma Glutamyltransferase (GGT)	> 3 times Upper Limit of Normal Range
Total Bilirubin	> 3 times Upper Limit of Normal Range

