11.9 Appendix 9: Liver Safety

Phase III-IV liver chemistry stopping and follow-up criteria have been designed to assure patient safety and evaluate liver event etiology (in alignment with the FDA premarketing clinical liver safety guidance). Phase III-IV liver chemistry stopping criteria 1-5 are defined below. Investigators may at their discretion refer patients meeting liver safety criteria below to a specialist who may determine the appropriate or medically necessary additional or confirmatory laboratory tests or procedures as required by the protocol or otherwise deemed necessary (e.g. liver imaging).

1. ALT \geq 3xULN and bilirubin \geq 2xULN (35% direct bilirubin) (or ALT \geq 3xULN and INR $>$ 1.5, if INR measured).

Note: if serum bilirubin fractionation is not immediately available, withdraw study drug for that patient if ALT \geq 3xULN and bilirubin \geq 2xULN. Serum bilirubin fractionation should be performed if testing is available. If testing is unavailable, record presence of detectable urinary bilirubin on dipstick, indicating direct bilirubin elevations and suggesting liver injury.

2. ALT \geq 8xULN.
3. ALT \geq 5xULN but $<$ 8 xULN persists for \geq 2 weeks.
4. ALT \geq 3xULN if associated with symptoms (new or worsening) believed to be related to hepatitis (such as fatigue, nausea, vomiting, right upper quadrant pain or tenderness, or jaundice) or hypersensitivity (such as fever, rash or eosinophilia).
5. ALT \geq 5xULN but $<$ 8 xULN and cannot be monitored weekly for \geq 2 weeks.

When any of the liver stopping criteria 1-5 is met do the following:

- **Immediately** discontinue blinded study medication/investigational product for that patient.
- Report the event to IQVIA within 24 hours of learning its occurrence.
- Complete the liver event CRF and SAE data collection tool if the event also meets the criteria for an SAE. All events of ALT \geq 3xULN and bilirubin \geq 2xULN (35% direct bilirubin) (or ALT \geq 3xULN and INR $>$ 1.5, if INR measured); INR measurement is not required and the threshold value stated will not apply to patients receiving anticoagulants), termed 'Hy's Law' must be reported as an SAE (excluding studies of hepatic impairment or cirrhosis).

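### The SAP's laboratory tables cannot show, by arm, how many patients met the protocol's combined ALT and bilirubin criterion

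*SAP*

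**What the plan says.** Protocol 11.9 lists five liver chemistry criteria. The first is ALT at or above 3x ULN with bilirubin at or above a limit printed as "2xULN (35% direct bilirubin", or ALT at or above 3x ULN with INR above 1.5 where INR was measured. The appendix labels these events Hy's Law, asks for a liver event form, and says that they "must be reported as an SAE (excluding studies of hepatic impairment or cirrhosis".

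SAP 17.2.1 classes each quantitative result as low, normal or high against the reference range, where "High: Above the upper limit of the laboratory reference range". It adds that clinically significant chemistry values "will also be identified in accordance with the predefined markedly abnormal criteria as presented in Table 4". In that table the limit for total bilirubin is "> 3 times Upper Limit of Normal Range", and ALT has the same limit.

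SAP 17.2 lists the outputs: values and changes by visit, incidence and shift by normal range, "Shift from baseline according to markedly abnormal criteria (for quantitative measurements and categorical measurements", and "Listing of patients meeting markedly abnormal criteria". It also says: "Viral serology, COVID-19 sample, chemistry and hematology will be listed". SAP 17.7 repeats the markedly abnormal output, for selected chemistry parameters, in the Extended Safety Set.

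**The concern.** The protocol criterion is a joint condition within one patient, with bilirubin cut at 2x ULN and limits that include the boundary. Table 4 handles each parameter separately, cuts bilirubin at 3x ULN and excludes the boundary. A reader of the laboratory tables who wants to know how many patients per arm met the protocol's own criterion will not find the number.

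This trial has few other places to look for it. SAP 4.1 says there is no data monitoring committee. Protocol 8.7.6 names no adverse events of special interest. The SAP text specifies no output for the liver event form, and SAP 18 does not name that form among data not presented. Exclusion 12 in Protocol 5.2 admits patients with chronic stable hepatitis B or C, so some may enter with liver disease, which makes a clear comparison between arms more useful.

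**Working it through.** The plan states no figure to reproduce on this point. The check applies both sets of rules to the same test values.

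**Rules** (values in multiples of ULN)

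- Protocol 11.9, criterion 1, bilirubin arm: ALT ≥ 3 and bilirubin ≥ 2. The direct-fraction qualifier is left aside here.
- SAP Table 4: ALT flag if ALT > 3; bilirubin flag if bilirubin > 3.
- SAP normal-range class: bilirubin High if > 1.

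| ALT | Bilirubin | Protocol criterion | Table 4 ALT flag | Table 4 bilirubin flag | Bilirubin range class |
|---|---|---|---|---|---|
| 3.0 | 2.0 | met | no | no | High |
| 3.5 | 2.0 | met | yes | no | High |
| 3.5 | 2.5 | met | yes | no | High |
| 3.5 | 3.0 | met | yes | no | High |
| 8 | 2.9 | met | yes | no | High |
| 3.0 | 3.5 | met | no | yes | High |
| 3.5 | 3.1 | met | yes | yes | High |
| 2.9 | 3.5 | not met | no | yes | High |
| 3.5 | 1.5 | not met | yes | no | High |

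**What this shows**

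1. Seven of the nine pairs meet the protocol criterion. Both Table 4 flags are on in only one of them (3.5 with 3.1).
2. The pairs 3.5 with 2.5 and 3.5 with 1.5 give identical flags and the same range class, yet the first meets the criterion and the second does not. The SAP categories cannot separate them.
3. The pair 3.0 with 2.0 meets the criterion and raises no Table 4 flag.

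**Why lowering the bilirubin cut is not enough.** Suppose a patients in an arm have ALT ≥ 3x ULN and b patients have bilirubin ≥ 2x ULN. When a + b does not exceed the arm size, the number with both can be anything from 0 to the smaller of a and b. With a = 1 and b = 1 the joint count is 0 or 1: two patients with one abnormality each, or one patient with both. Separate tables give a and b but not the joint count.

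**Are the data there?** Protocol 11.3, Table 11, includes ALT and total and direct bilirubin, so the bilirubin arm can be derived. INR is not in that table, so the INR arm can be shown only where INR happened to be measured.

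**The case against.** The strongest reply is that nothing is hidden. Any bilirubin above ULN is classed High and enters the normal-range tables. Any patient with ALT above 3x ULN enters the markedly abnormal listing whatever the bilirubin, and the full chemistry listing gives the bilirubin value. Protocol 9.4.2 also promises that out-of-range values are highlighted. A case handled under Protocol 11.9 should appear among the serious TEAEs (SAP 17.1.3) and the TEAEs leading to discontinuation of study medication (SAP 17.1.2). Protocol 9.4.2 promises no joint liver table, so the SAP breaks no commitment. A per-patient criterion and a descriptive per-parameter category can properly use different cut-offs. The shells, which SAP 8 says set the format and content of tables and listings, were not supplied and might hold such a table.

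Most of this stands, and it limits the point. A reader might infer that these cases would go undetected or unreported, or that the SAP contradicts the protocol. The documents support neither reading. In the test values, the only case that reaches neither Table 4 flag sits exactly on the ALT boundary, and the full chemistry listing still contains it.

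What the reply does not supply is a count by arm. Listings allow cases to be found by hand, but SAP 17.2 does not say that bilirubin is shown beside ALT in the markedly abnormal listing. Tables by system organ class and preferred term depend on how the site recognised and named the event, not on the laboratory values.

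**Conclusion.** The point holds as a gap in tabulation. As written, the SAP produces no laboratory summary from which the number of patients meeting the protocol's combined criterion can be read by arm. There are three causes: the 3x ULN bilirubin cut, the limit that excludes ALT of exactly 3x ULN, and above all the absence of any output that joins the two parameters within a patient.

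The size is small. No efficacy conclusion is touched, the data are collected, and nearly every case can be found by hand. The documents give no expected rate. I assume few cases, which makes listings workable but also makes an exact joint count worth having. The conclusion rests on the SAP text; a joint table in the shells would answer most of it. It concerns reporting only and takes no view on which clinical criterion is right.

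**What to change.** Reconcile SAP 17.2.1 with Protocol 11.9 for reporting purposes:

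- Add a total bilirubin category at or above 2x ULN to Table 4. The existing 3x category can stay.
- Make the ALT 3x limit inclusive. AST need not be added for this purpose, because criterion 1 uses ALT.
- Add a count by treatment arm, and a listing, of patients with ALT at or above 3x ULN and total bilirubin at or above 2x ULN within a time window stated before unblinding. Say whether unscheduled and repeat samples count, since SAP 6.3 keeps unscheduled values out of by-visit summaries.
- Show the direct bilirubin fraction for each listed patient, and INR where measured, so that the count can be set against the protocol definition and the reported SAEs.
- Produce these for the Safety Set and the Extended Safety Set.

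The cost is one within-patient derivation, one table and one listing, run in two sets. No new data are needed. If the shells already contain such an output, a sentence in SAP 17.2 pointing to it, with the cut-offs and window, is enough.
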